5.2. Adverse Events

The verbatim terms used in the eCRF by investigators to identify adverse events will be coded using the latest version of the Medical Dictionary for Regulatory Activities (MedDRA) at the time of database lock. Any AE occurring on or after the initial administration of ATIMP is considered to be treatment-emergent. All reported treatment-emergent adverse events will be included in the analysis. For each adverse event, the number and percentage of subjects who experience at least 1 occurrence of the given event will be summarized by age group, dose level and overall.

Summary tables will be provided for the frequency and incidence of subjects experiencing the following treatment-emergent adverse events:

- AEs
- Serious AEs (SAEs)
- AEs leading to termination of study participation
- AEs by severity
- AEs by relationship to ATIMP
- AEs by relationship to ATIMP surgery
- Death
- AEs of interest related to ocular inflammation

Summaries of adverse events by system organ class and dictionary-derived (preferred) term will also be provided.

In addition to the summary tables, accompanying listings will be provided for subjects who experience:

AEs

- SAEs
- AEs leading to termination of study participation
- Death (if any)
- AEs of interest related to ocular inflammation.

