4.1.5.6 Risk of adverse effects of short-term corticosteroids

Candidates will be screened for contra-indications to transient immune suppression by corticosteroids; in particular, a history of uncontrolled hypertension, diabetes mellitus, tuberculosis, renal impairment, osteoporosis, gastric ulceration, severe affective disorder and immunocompromised status. The possibility of steroid-induced adverse effects will be monitored regularly. In particular, blood pressure and blood glucose will be measured, as will renal function and liver function (at baseline, 1 day, 7 days, 2 weeks and 4 weeks after surgery).

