5.4.2.2.1 Pre-operative Procedures

For prophylaxis against potential intraocular immune responses to the ATIMP, participants will be prescribed a course of oral prednisolone, commencing at a daily dose of 0.5 mg/kg one week prior to ATIMP administration; 1mg/kg for the first week following administration, 0.5mg/kg for the second week, 0.25mg/kg for the third week and 0.125mg/kg for the fourth week.

Gene Therapy for Achromatopsia (CNGB3)

Preoperative procedures and intraocular administration of ATIMP will be as described in the Gene Therapy for Achromatopsia (CNGB3) study manual.

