5.4.9 Protocol Discontinuation

5.4.9.1 Participant Withdrawal

In consenting to the trial, participants consent to ATIMP administration, trial follow-up and data collection.

As participation is entirely voluntary, participants may choose to withdraw from the trial at any time without penalty or loss of benefits to which they would otherwise be entitled. Although not obliged to give a reason for withdrawal, a reasonable effort should be made to establish and document this in the withdrawal eCRF, whilst fully respecting the participants rights.

Should a participant withdraw from the study, a withdrawal eCRF documenting the reason for withdrawal (if provided) will be completed, in addition to the procedures and eCRF for the final visit (6 month) assessments, with the participant's consent. However, participants will be encouraged to participate in any of the planned schedule for the trial whilst arranging a visit for routine (annual) clinical follow-up.

Participants who withdraw prior to ATIMP administration will be regarded as off-protocol and their primary ophthalmologist will resume normal standard of care. Any participant who withdraws prior to administration of ATIMP may be replaced in the study.

Participants who withdraw from the study after ATIMP administration will be strongly encouraged to have follow-up investigations with their consent, so that the consequences of ATIMP administration can be documented and the data analysed. The CMT may choose to replace a participant who withdraws after ATIMP administration.

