5.11.3.6 Notifications

5.11.3.6.1 Notifications by the Investigator to [REDACTED]

All adverse events will be recorded in the hospital notes and the eCRF from the date of written informed consent until last study visit.

Investigators should notify [REDACTED] of any SAEs and SARs occurring during this period. After the last visit, any SAE reported to the investigator and considered causally related to trial treatment should be reported as part of the follow up study. For any participants that do not go into the follow up study, then SAEs that occur after the end of the trial and that may be attributed to ATIMP administration should be reported to the relevant regulatory agencies.

[REDACTED] must be notified of all SAEs and SARs within 24 hours of the investigator becoming aware of the event. The investigator will respond to any SAE queries raised by [REDACTED] as soon as possible.

The SAE form must be completed by the investigator (the consultant named on the delegation of responsibilities list who is responsible for the participant's care) with attention paid to the grading and causality of the event. In the absence of the responsible investigator, the SAE form should be completed and signed by a member of the site trial team and emailed as appropriate within the timeline. The responsible investigator should check the SAE form at the earliest opportunity, make any changes necessary, sign and then email to [REDACTED]. Systems will be in place at the site to enable the investigator to check the form for clinical accuracy as soon as possible.

The minimum criteria required for reporting an SAE are the trial number and date of birth, name of reporting investigator and sufficient information on the event to confirm seriousness. Any further information regarding the event that is unavailable at the time of the first report should be sent as soon as it becomes available.

The SAE form must be scanned and sent by email to the trial team on

[REDACTED]

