3. ANALYSIS DEFINITIONS

3.1. Analysis Sets

For safety analyses, the safety analysis set includes all enrolled subjects who were administered ATIMP.

For efficacy analyses, the full analysis set includes all enrolled subjects who were administered ATIMP and have both a baseline and at least 1 visit after ATIMP administration.

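### The SAP's adverse event and disposition tables begin at vector injection and cover injected participants only, so the week of trial-mandated prednisolone before injection is not tabulated

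*SAP*

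**What the plan says.** SAP 5.2 defines the window: "Any AE occurring on or after the initial administration of ATIMP is considered to be treatment-emergent". It then says "All reported treatment-emergent adverse events will be included in the analysis", and introduces the tables with "Summary tables will be provided for the frequency and incidence of subjects experiencing the following treatment-emergent adverse events". The list that follows includes serious events, events leading to termination of participation, and deaths. Under SAP 3.1, "the safety analysis set includes all enrolled subjects who were administered ATIMP". SAP 4.3 reports disposition, with reasons for discontinuation, on that same set.

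Protocol 5.4.2.2.1 prescribes oral prednisolone "commencing at a daily dose of 0.5 mg/kg one week prior to ATIMP administration", and Protocol 5.4.1.5 gives the same pre-injection week. Protocol 4.1.5.6 treats steroid harm as a trial risk: "The possibility of steroid-induced adverse effects will be monitored regularly". Protocol 5.11.3.6.1 has adverse events entered in the eCRF "from the date of written informed consent until last study visit". On people who stop before injection, Protocol 5.4.9.1 says "Participants who withdraw prior to ATIMP administration will be regarded as off-protocol". Both that section and 5.3.1.6.3 allow them to be replaced.

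**The concern.** Participants begin a systemic drug, solely because they are in the trial, a week before the point at which the SAP starts counting harm. The protocol identifies that drug's adverse effects as a risk and collects the events, but the SAP's stated rules leave two groups out of the tables:

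- **Injected participants with an earlier event.** An event with a complete onset date between the first prednisolone dose and injection is not treatment-emergent, so no adverse event table counts it.
- **Participants who started prednisolone or surgery but were never injected.** They are outside the safety set, so they are absent from the adverse event tables, the disposition table and the denominators. They may also be replaced.

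A reader of the tables could not distinguish an absence of harm before injection from harm that was not tabulated.

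**Working it through.** The documents give no figure for this gap, so there is none to reproduce. The check applies the SAP's rules to the protocol's schedule and then sizes the uncovered period.

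**Inputs**

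- Prednisolone or prednisone, mg/kg daily, one week at each level: 0.5 before injection, then 1, 0.5, 0.25 and 0.125 after it (Protocol 5.4.1.5 and 5.4.2.2.1).
- Maximum enrolment: 36 (Protocol 5.7).
- Start of the adverse event window: the day of injection (SAP 5.2; Study Day 1 in SAP 3.3).
- Safety set and disposition: injected participants (SAP 3.1 and 4.3).

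**Where an event would appear under the SAP**

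| Case | AE summary tables | Disposition table |
|---|---|---|
| Event dated after injection | Yes | Participant counted |
| Event fully dated in the pre-injection week, participant later injected | No | Participant counted |
| Event in the pre-injection week, participant never injected | No | Participant absent |

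Partial dates behave differently. Under SAP 3.6, an event with only the onset day missing, in the month of injection, is set to the injection day, or to the resolution day if that is earlier and in the same month. Some pre-injection events with incomplete dates would then be counted, while the same events with complete dates would not.

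**Exposure outside the adverse event window**

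- Days: 7 before + 28 after = 35; 7 / 35 = 20%.
- Cumulative dose: 7 × (0.5 + 1 + 0.5 + 0.25 + 0.125) = 7 × 2.375 = 16.625 mg/kg. Pre-injection part: 7 × 0.5 = 3.5 mg/kg; 3.5 / 16.625 = 21.1%.
- At the maximum enrolment: 36 × 7 = 252 person-days.

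**Participants outside the safety set.** The documents do not give this number. Assume k people started prednisolone without being injected, beside 36 injected; the missing share is k / (36 + k).

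| k (assumed) | Share missing |
|---|---|
| 0 | 0 / 36 = 0% |
| 1 | 1 / 37 = 2.7% |
| 2 | 2 / 38 = 5.3% |
| 3 | 3 / 39 = 7.7% |

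**Chance that the week contains any event.** The documents give no event rate. For an assumed per-person risk p, the chance of at least one event in 36 people is 1 − (1 − p)^36.

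| p (assumed) | Chance of at least one event |
|---|---|
| 1% | 30% |
| 3% | 67% |
| 5% | 84% |
| 10% | 98% |

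**The case against.** The strongest reply is that the primary objective concerns the safety of the vector. Prednisolone is a licensed non-investigational product, and starting treatment-emergence at the investigational product suits that objective. This stands: the existing definition and set should remain for the primary outcome and the dose-level tables. It does not explain why a protocol-required exposure with a named risk has no table of its own.

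Second, the events are recorded and need not be invisible. This also stands:

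- The adverse event and serious adverse event listings in SAP 5.2 are not expressly limited to treatment-emergent events, so pre-injection events may appear there.
- Serious events must be notified within 24 hours (Protocol 5.11.3.6.1).
- A baseline symptom that worsens after injection counts as an adverse event (Protocol 5.11.3.1).
- Table shells are in a separate document (SAP 1), which may say more.

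These points narrow the gap to the tables. They do not remove it, because the SAP text itself sets the exclusions.

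Four stronger readings are tempting, and the documents do not support them.

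- **That the omission selectively removes people harmed badly enough not to be injected.** That would follow only if such people exist, and nothing shows that anyone was stopped by prednisolone or had surgery abandoned. Protocol 5.4.2.2.2 describes the check for retinal breaks after delivery of the vector. Because Study Day 1 is the calendar day of injection, an intraoperative event in an injected participant would probably be counted.
- **That no test can fall in the prednisolone week.** Protocol Table 2 schedules baseline vital signs and biochemistry in a window of up to six months before injection. It neither guarantees nor prevents a visit in that week. Day 1 results may reflect steroid effects in injected participants if baseline came before the steroid, but mixed with those of surgery and the post-injection steroid.
- **That each withdrawal before injection is a serious event.** A withdrawal need not meet the protocol's definition of serious.
- **That steroid-related events can be picked out by attribution.** Protocol 5.11.3.5.3 captures causality for the vector and the surgery only.

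**Conclusion.** The gap is real but limited to tabulation. Under the SAP's stated rules, fully dated adverse events between the first prednisolone dose and injection, and anyone who started prednisolone or surgery without being injected, are left out of the summaries described above. The uncovered week is 20% of scheduled steroid days and 21.1% of the scheduled cumulative dose. These are shares of exposure, not estimates of harm; about 80% of steroid exposure, including the peak dose, lies inside the window.

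The number of people concerned may be zero. The range of 0% to 7.7% rests entirely on the assumption of 0 to 3 uninjected participants beside 36 injected. A reader might infer that the primary safety result or the dose decisions are biased. They are not touched, because the primary outcome and dose-limiting events count only events after administration that are at least possibly related to the vector. The point is a cheap improvement in the completeness of safety reporting.

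**What to change.** Keep the vector-administered set for the primary outcome and the dose-level tables, and add the following to the SAP:

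1. In 5.2, one supplementary table and one listing of adverse events and serious adverse events with onset from the first trial prednisolone dose to injection. Include everyone who took that dose, whether or not later injected, and include events regardless of attributed cause.
2. In 4.3, a disposition line for participants who started prednisolone or surgery but did not receive the vector, with the reason.
3. In 5.2, a statement that the adverse event and serious adverse event listings cover events from consent.

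The cost is SAP wording and a small amount of programming on data already in the eCRF. No visit, test or treatment rule changes. The added table may be empty, but an empty table would itself tell the reader that no such event was recorded.

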5.3. Clinical Laboratory Tests

Clinical laboratory tests will be displayed for the subjects included in the safety analysis set. Hematology, clinical chemistry, glucose, serology and polymerase chain reaction (PCR) laboratory tests will be presented.

Summary statistics of hematology and clinical chemistry observed values and change from baseline by parameter (unit) will be summarized by age group, dose level and overall.

All hematology and clinical chemistry values will be listed.

Serology data will be listed and summarized at each assessment by age group, dose level and overall.

All PCR values will be summarized by tissue and listed.

5.4. Vital Signs and Physical Examination Findings

Continuous vital sign parameters including height, weight, pulse, blood pressure (systolic and diastolic), pulse, respiration rate, arterial oxygen saturation, temperature will be summarized at each assessment time point. Change from baseline will be summarized through Week 24 using descriptive statistics (mean, standard deviation, median, minimum and maximum).

Individual physical examination data will be listed by subject.

5.5. Other Safety Parameters

All pregnancy test data will be listed.

6. EFFICACY

Unless otherwise specified, efficacy analyses will be based on the full analysis set and statistical tests will be interpreted at a 2-sided nominal significance level of 0.05, with confidence intervals presented at a 2-sided level of 95%.

6.1. Changes to the SAP

The original SAP (dated 24 May 2019) described analyses of the test-retest variation for each visual function assessment, however, this will not be assessed given that the assessment of safety is the primary objective of the study and the secondary objectives for efficacy focus on the effect of the treated eye compared to the untreated eye. The statistics for the test-retest do not fit the purposes of the stated objectives and are not appropriate for the goals of the study.

6.2. Analysis Methods

Summaries by age group, dose level and time point (and study eye when appropriate) using descriptive statistics will be provided for each outcome. Descriptive statistics such as mean, median, standard deviation, minimum, and maximum will be used to summarize continuous variables, and counts and percentages will be used to summarize categorical variables; 95% CIs may be provided for descriptive statistics. Data from each individual will also be plotted across time by age group and dose level for the treated eye compared to the untreated eye, if available. Change from baseline will be summarized, if appropriate.

Mixed linear effects models may be used to assess differences between the treated and the untreated eye with covariates including age group, dose level, time and the interaction of dose level by time. An unstructured correlation structure will be used to model within-subject correlations when possible. Possible transformations of the response (i.e., logarithm) may also be considered for some outcomes.

Sensitivity analyses with demographics such as sex and race may be explored.

Quality of life patient reported outcome measures may be used to correlate a subject's feeling about their own well-being with clinical observations. The IVI-C and IVI-A will be summarized by the 3 domains of reading and accessing information, mobility and independence, and emotional well-being. The EQ-5D-5L⁴ and EQ-5D-Y⁵ will also be summarized (see Attachment 1 for details).

For specialized ophthalmologic assessments, data may be analyzed by the expert team member(s) who are best qualified to analyze and interpret those assessments. Final data will be reported descriptively.

REFERENCES

- Goldstein JE et al. Calibrating the impact of vision impairment (IVI): creation of a sample-independent visual function measure for patient-centered outcomes research. Translational Vision Science & Technology; December 2018; Vol.7, 38
- 2. Lamoureux EL et al. The impact of vision impairment questionnaire: an evaluation of its measurement properties using Rasch analysis. Invest Ophthalmology & Vision Science; November 2006; 47(11):4732-41
- 3. Lamoureux EL et al. The impact of vision impairment questionnaire: an assessment of its domain structure using confirmatory factor analysis and Rasch analysis. Invest Ophthalmology & Vision Science. March 2007; 48(3):1001-6

1. DESCRIPTION OF QUESTIONNAIRE DATA

The impact of visual impairment (IVI) vision-related quality of life (VRQoL) questionnaire queries the level of restriction of participation in common daily experiences due to visual impairment. For this study, there will be 2 sets of IVI questionnaires. The adults will complete a 28-item questionnaire (IVI-A) and the children will complete a 24-item questionnaire (IVI-C). The impact of photoaversion (extreme sensitivity to light) on activities of daily living (ADLs) will be assessed with the Photoaversion (PA) patient-reported questionnaire.

For adults, the IVI questionnaire covers a broad range of issues in 3 separate domains of functioning. The domains and the items that they contain are:

- Reading and accessing information domain contains items 1, 3, 5, 6, 7, 8, 9, 14, 15. Items 1, 3 and 5 to 9 will be rated on a 5-level scale (0 = a lot, 1 = a fair amount, 2 = a little, 3 = not at all and 8 = don't do this for other reasons). Items 14 and 15 will be rated on a 4-level scale (0 = a lot, 1 = a fair amount, 2 = not at all and 8 = don't do this for other reasons).
- Mobility and independence domain contains items 2, 4, 10, 11, 12, 13, 16, 17, 18, 19, 20. Items 2, 4 and 10 to 13 will be rated on a 5-level scale (0 = a lot, 1 = a fair amount, 2 = a little, 3 = not at all and 8 = don't do this for other reasons). Items 16 to 20 will be rated on a 4-level scale (0 = a lot, 1 = a fair amount, 2 = a little and 3 = not at all).
- Emotional well-being domain contains items 21 to 28. These items will be rated on a 4-level scale (0 = a lot of the time, 1 = a fair amount of time, 2 = a little of the time and 3 = not at all).

The EQ-5D is a standardized measure of health status. The EQ-5D-5L questionnaire will be completed by adults while EQ-5D-Y will be completed by children.

- The 5 dimensions of both questionnaires are:
 - Mobility
 - Self care
 - Usual activities
 - Pain/discomfort
 - Anxiety/depression
- Each of the dimensions of EQ-5D-5L have 5 levels:
 - Level 1: indicating no problems
 - Level 2: indicating slight problems
 - Level 3: indicating moderate problems

- Level 4: indicating severe problems
- Level 5: indicating extreme problems
- Each of the dimensions of EQ-5D-Y have 3 levels:
 - Level 1: indicating no problems
 - Level 2: indicating some problems
 - Level 3: indicating a lot of problems

In addition, there are 13 questions focused on photoaversion questionnaire.
